This proposed study will thoroughly examine the effect of Paro intervention on biomarkers (such as oxytocin level, dopamine and HRV), and cognitive function, and mental well-being for specific attachment orientation older adults with dementia. This is the first study we know of to utilize a rigorous research design to examine the effect of Paro intervention and explore the linkages between biomarkers and psychological well-being for older people with dementia. The findings of this study will provide strong evidence and advance knowledge of the mechanism of Paro intervention in LTC of Taiwan and be able to link this result to international studies. The findings of the research will publish in international journals.

III. Background

Serious issues in the mental health of older populations have shown in LTC facilities worldwide. In Taiwan, the prevalence of dementia was 7.78% in older adults. Many older adults with dementia were admitted into long-term care due to BPSD. However, older adults moved into LTC would vitiate quality of life and mental health due to insufficiency of social network. These will increase loneliness. Evidence has shown

that there were positive correlations between depression and loneliness (Cacioppo, Hughes, Waite, Hawkey, & Thisted, 2006; Tiikkainen & Heikkinen, 2005). An empirical study has been demonstrated that loneliness is an important influence factor that increased depression for older adults (Chou, 2004). These issues merit to pay more attention to find effective strategies. Despite this, there is limited research to explore the mechanism of effective interventions on depression and loneliness among older adults living in LTC.

Regarding the development of the human emotional relationship, the attachment is an important mechanism for interpersonal interaction. An individual may have a higher risk to suffer from depression or loneliness when she/he cannot develop a close attachment relationship (i.e. presenting attachment anxiety or attachment avoidance) (Burnette, 2008; Schiffrin, 2014; Wei, 2005). Consequently, there is a significant correlation between interpersonal attachment orientations and mental health.

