This is a repeated measures study that is a pilot randomized controlled trail, four parallel groups, and double-blind design. It is used to examine the effects of Paro intervention on cognition, executive functions, and mental well-being for specific attachment older adults with dementia at before, during and after the intervention. A mixed between-within subjects analysis of variance design will be used to assess the immediate effects of the 6-week Paro intervention on cognitive, executive and three mental well-being related variables for different attachment orientations of older adults living LTC facilities. Outcomes of interest measures will include dopaminergic activities variations by FTT and HRV changes at three time points: before the intervention (T0), middle of intervention (week-3, T1), the end of intervention (week-6, T2), and 1 month after the intervention (T2). Furthermore, the change of oxytocin level will be assessed at baseline and the end of the intervention.

The purpose of this study is to examine the effect of Paro intervention on neurobiologically changes for older adults with dementia in LTC. The research design is shown in Table1.

Table 1 Research design for Paro intervention

Group	Subgroup	T0	Intervention	T1	T2	T3
Security	Experiment	O ₁	X	O ₂	O ₃	O ₄
	Control	O ₁		O ₂	O ₃	O ₄

Experiment group: Paro intervention; Control group; O₁: Baseline; O₂: Week 3; O₃: Week 6; O₄: Week 10

4. Sample size, Sampling, Settings, and Participants Recruitment

There are 120 participants will be recruited into this pilot randomized controlled trial from LTC facilities in southern Taiwan. Older adults will be randomly assigned to four groups: experimental group or control group. The purpose of sampling will be used to allocate 60 participants either to the experimental group or the control group using computer generated sampling. Contact has been made with the Directors of the LTC facilities who have expressed their interest in being involved in the study. Directors will invite older adults who meet the inclusion criteria to participate in this study.

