The aims of this study is to examine the effect of the Paro intervention on cognitive, executive functions and mental well-being for older people with dementia.

2. Objectives

- (6) To examine the effect of Paro intervention on cognitive and executive functions for older people with dementia.
- (7) To examine the effect of Paro intervention on depression for older people with dementia.
- (8) To examine the effect of Paro intervention on loneliness for older people with dementia.
- (9) To examine the effect of Paro intervention on mental well-being for older people with dementia.

3. Research design

This is a repeated measures study that is a randomized controlled trial, four parallel groups, and single-blind design. It is used to examine the effects of Paro intervention on cognition, executive functions, and mental well-being for older adults with dementia at before, during and after the intervention. A mixed between-within subjects analysis of variance design will be used to assess the immediate effects of the 6-week Paro intervention on cognitive, executive and three mental well-being related variables for different attachment orientations of older adults living LTC facilities. Outcomes of interest measures will include cognitive and executive functions, and depression, loneliness, and mental well-being at three time points: before the intervention (T0), middle of intervention (week-3, T1), the end of intervention (week-6, T2), and 1 month after the intervention (T2). Secondary outcome is interest in the impacts of the Paro intervention on psychological outcomes for different attachment style of older adults with dementia. The Revised Adult Attachment Scale Chinese version (RAAS-C) will be used to classify the attachment types of the elderly. A sub-group analysis will be conducted to further understand the changes in the physical and mental health of the elderly with different attachment types after receiving Paro intervention.

The purpose of this study is to examine the effect of Paro intervention on cognitive, executive, depression, loneliness, and mental well-being depression and loneliness for

older adults with dementia in LTC. The research design is shown in Table 1.

Table 1 Research design for Paro intervention

Group	T0	Intervention	T1	T2	T3
Experiment	O ₁	X	O ₂	O ₃	O ₄
Control	O ₁		O ₂	O ₃	O ₄

4. Sample size, Sampling, Settings, and Participants Recruitment

The same with study 1.

5. Intervention

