To probing the change of the markers, a series of paired sample t-test will be used for each group. To testing the research hypothesis, a mixed designed generalized linear model (GLM) will be employed to test the effects of arms on the differences between the pre and post-test in relation to outcome measures, including oxytocin level, dopamine and HRV changes for different attachment orientations of older adults living LTC facilities. In order to increase precision in estimating the effect of interest, the possible confounding effects of the covariates, such as age, education, etc, will be used to take into account as covariate in the model. The effect size will be calculate to show the magnitude and direction of the effect in the attachment-specific group relative to the control for each outcome variable. In order to identify the optimal duration of clinical application for this intervention, a trend analysis will be conducted. Exploratory additional analysis will be conducted to test the interaction between intervention, and potential biomarker on clinical evaluation. A p value $< .05$ will be taken as the level of statistical significance. The 95% confidence interval around the differences will be calculated.

II. Expectation Outcome

We expect to identify positive effect of Paro intervention on cognitive, executive functions, depression, loneliness, and mental well-being for older adults with dementia.

III. Ethical Considerations

Ethics approval for both phases of the study will be sought from Cheng-Kung University Human Research Ethics Committee and prior to the commencement of the study. Ethics approval for the study will also be sought from the participating LTC facilities in Taiwan prior to the commencement of the study. The researcher will inform the participants about the aims and objectives of the research study and what their participation will involve. Participants will be assured that (a) their participation will be on a voluntary basis and they are under no obligation to participate; and (b) they are free to withdraw from the study at any time without explanation, penalty or compromising their relationship with the LTC. A signed consent form will be sought from each participant. There are no foreseeable risks associated with participation in the intervention for participants.

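### Study 3 asks about the effect of Paro by attachment style but writes no arm-by-attachment test, and sub-group results alone cannot answer that question

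*Combined protocol and SAP*

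**What the plan says.** Study 3, I.3 Research design, sets the question: "Secondary outcome is interest in the impacts of the Paro intervention on psychological outcomes for different attachment style of older adults with dementia". The same section says how participants are typed, "The Revised Adult Attachment Scale Chinese version (RAAS-C) will be used to classify the attachment types of the elderly", and what follows: "A sub-group analysis will be conducted to further understand the changes in the physical and mental health of the elderly with different attachment types", with the changes being those seen after Paro. Study 3, I.7, Table 2 schedules the RAAS-C at baseline only. I found no statement of the number of types, the cut-offs or the expected shares.

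Study 3, I.8 Data analysis, plans:
- paired t-tests in each group;
- a mixed-design general model testing the arms on pre-post differences, with age and education given as example covariates;
- an effect size to show "the magnitude and direction of the effect in the attachment-specific group relative to the control for each outcome variable".

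The model sentence in I.8 names oxytocin, dopamine and HRV, which are Study 1's outcomes. Study 3's own outcomes fall under the mixed ANOVA mentioned in I.3. Both sentences refer to different attachment orientations, but neither lists model terms. The only interaction named anywhere is between the intervention and a potential biomarker, and it is exploratory.

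**The concern.** Whether Paro works differently by attachment type is a question about the difference between two treatment effects. What is written produces separate results: a change within each type, a p-value within each group, and an effect size for an attachment group. None of these estimates the difference. A reader of the results would be left to compare a significant finding in one type with a non-significant finding in another, and that pattern arises often by chance when the effect is the same in both.

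There is a second problem, which depends on what the control means in I.8. If one type's Paro participants are set against the whole control arm, randomisation no longer protects the comparison, because the two sides differ in attachment mix. The protocol's Background (section III) holds that "there is a significant correlation between interpersonal attachment orientations and mental health", so types may plausibly also differ in their course without Paro.

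At stake is an attachment-specific claim about whom Paro helps, in a document that expects its results to be promoted as a care model in long-term facilities.

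**Working it through.** **Inputs from the documents.** Study 1, II.4, which Study 3 adopts: "There are 120 participants will be recruited into this pilot randomized controlled trial from LTC facilities in southern Taiwan", and the sampling is to "allocate 60 participants either to the experimental group or the control group using computer generated sampling". So 2 × 60 = 120. No effect size, SD, power or dropout is given, so the 120 cannot be re-derived. No stratification by attachment is stated. A p-value below .05 "will be taken as the level of statistical significance"; I take it as two-sided.

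**Assumptions.** Two attachment types of equal size, so 30 per arm in each; the same true effect d (in SD units) in both; independent participants, although Paro is given in groups of 6 to 8.

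**Step 1: chance that exactly one type is significant.** Power within a type with n = 30 per arm is p = Φ(d√(n/2) − 1.96) + Φ(−d√(n/2) − 1.96), with √(30/2) = 3.873. The chance that one type is significant and the other is not is 2p(1 − p).

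| d | p in each type | 2p(1 − p) | simulated | interaction test, simulated |
|---|---|---|---|---|
| 0 | 0.050 | 0.095 | 0.094 | 0.051 |
| 0.3 | 0.213 | 0.336 | 0.328 | 0.049 |
| 0.5 | 0.491 | 0.500 | 0.502 | 0.049 |
| 0.7 | 0.774 | 0.350 | 0.364 | 0.050 |

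The simulation used 40,000 runs, t-tests within types and an F test for arm by attachment. The discordance covers either direction; one named direction has half the chance, for example 25% at d = 0.5.

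**Step 2: other splits (assumed).** For d = 0, 0.3, 0.5 and 0.7, the chance that some but not all types are significant is:
- two types of 42 and 18 per arm: 9.5%, 34%, 55%, 46%;
- three types of 20 per arm: 14%, 40%, 69%, 72%;
- four types of 15 per arm: 19%, 43%, 72%, 87%.

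The interaction test stays between 4.8% and 5.1% in every scenario simulated.

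**Step 3: paired tests by type inside the Paro arm.** Suppose both types change by 0.3 SD of the change score, which needs no Paro effect. With 30 per type, p = 0.376 and 2 × 0.376 × 0.624 = 0.47.

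**Step 4: one type against the whole control arm.** Let natural change differ by g SD between two types, let the type have share s, and let Paro have no effect. The bias is g(1 − s), with SE = √[1/(60s) + (1 + g²s(1 − s))/60].

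| g (assumed) | s = 0.5: bias, false-positive rate | s = 0.3: bias, false-positive rate |
|---|---|---|
| 0.3 | 0.15 SD, 10% | 0.21 SD, 12% |
| 0.5 | 0.25 SD, 20% | 0.35 SD, 25% |
| 0.8 | 0.40 SD, 41% | 0.56 SD, 54% |

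With a control of the same type, this bias is zero in expectation.

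**Step 5: precision of the interaction.** With 30 per cell, SE = √(4/30) = 0.365 SD. Detectable at 80% power: 2.80 × 0.365 = 1.02 SD. For the main effect, 2.80 × √(2/60) = 0.51 SD. Power to detect a 0.5 SD difference in effect between the types is 28%.

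**The case against.** The strongest reply is that the plan may intend the right analysis and has only failed to write it out. Study 1, II.3, Table 1 nests Experiment and Control under a row labelled Security, which is a same-type control. Study 1 and Study 3 both speak in places of four parallel groups, which would fit two arms by two attachment types. The ANOVA and the general model are both mentioned in connection with attachment orientations. No sentence says that a differential effect will be concluded from discordant p-values, and I.8 promises effect sizes and 95% confidence intervals.

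Much of this stands, and it limits the point in four ways.
- A reader might infer that the interaction has been ruled out. The documents do not support that: the model terms are simply not listed.
- A reader might infer that the attachment comparison is confounded. That follows only if the control is the whole control arm, or if changes are compared between types within the Paro arm. Also, the Background reports a correlation with mental health, not a difference in change over time, so the values of g in Step 4 are assumptions.
- A reader might take 50% as the general error rate. It is the maximum of 2p(1 − p) for two types, reached near d = 0.5 with an equal split.
- A reader might take attachment type as a modifier to be the main question throughout. Study 3's own aim and objectives do not mention attachment, and Study 1's title treats attachment as something that may change.

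The reply does not remove the core. Study 3's Table 1 has no attachment row, no test between types is written, and an interaction is named where one was wanted, for a biomarker. Confidence intervals within types still do not estimate the difference between types.

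**Conclusion.** The point holds as a fault in the analysis specified for a stated secondary interest. As written, the plan yields sub-group results that cannot show a differential effect. With two equal types and a common true effect, exactly one type is significant in about 10% to 50% of trials over d = 0 to 0.7, against about 5% for one interaction test. These figures rest on the assumed number and sizes of types, on independent participants and on a two-sided 0.05 level. The noise argument applies whichever control is meant. The bias argument is conditional: it applies if the control is the whole control arm and disappears in expectation if the control is of the same type, so the text must say which. With 120 participants, even the correct analysis can only be exploratory.

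**What to change.** In Study 3, I.8, for each outcome:
- Fix the RAAS-C types and cut-offs before outcome data are seen.
- Fit one model on all randomised participants with arm, attachment, arm × attachment and the baseline value. Add time and its interactions where the outcome is measured repeatedly.
- Base any claim of an attachment-specific effect on the interaction estimate and its 95% CI.
- Report type-specific effects only as Paro minus control within the same type, and define the control that way in the effect-size sentence.
- Do not use before-after changes by type, or paired t-tests, as evidence of effect.
- Label the analysis exploratory.

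The cost is some wording and a few model terms; the RAAS-C is already scheduled at baseline, so no new data are needed. The downside is that claims will be weaker, because the interaction is imprecise: about 1.0 SD is detectable with 30 per cell (1.12 SD with a 70/30 split), against about 0.5 SD for the main effect.

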The inclusion criteria of elderly participants will be: (1) aged 65 years or over; (2) Mild to moderate dementia (3) an ability to communicate in Mandarin or Taiwanese; and (4) has been living in the LTC facility at least 3 months. Older adults who: (1) have severe difficulty in communication; (2) are totally dependent on carers for daily activity; (3) have a diagnosed infectious disease, severe dementia, and severe mental illness such as schizophrenia and delusional disorder, will be excluded from the study.

5. Intervention

Participants in the experimental group will receive a group (6-8 people as a group) , facilitated, and 30-minute weekly session Paro intervention for 6 weeks. The control group will receive care as usual activities, such as painting, drawing, and craft, which are provided by each facility.

6. Paro

Paro (Personal Assistive Robot), was developed by [name] in Japan. It has the appearance of a baby harp seal; the current version (V9) weighs 2.5 kilograms and is approximately the size of a new-born baby. Paro is equipped with an array of tactile sensors that monitor sound, light, temperature and touch via artificial intelligence software. Paro can show human-like emotional reactions when it feels surprised, happy, or angry, and it will cry when it is neglected or not receiving sufficient attention.

In this study, Paro will be used as a Robot-pet companionship intervention with the aim to improve mental health in terms of different attachment orientations. Robot-pet companionship interventions are based on human-animal interactions aimed at providing physiological, psychological, and social benefits (Robinson et al., 2015; Chang et al., 2013; Cohen-Mansfield et al., 2010; Shibata et al., 2004).

Figure 1. The images of Paro

7. Procedure of interaction records

Participants in experimental groups will receive a group, facilitated, 30-minute weekly session of Paro intervention. A trained research assistant (RA) give the Paro to the participants at the start of each session, repeating the same introductory script each time. The RA facilitate the participant interact with the Paro during the intervention, after 30 minutes RA will use the same ending script to end the session and goodbye to participants.

8. Outcome measures

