Participants in the experimental group will receive a group (6-8 people as a group), facilitated, and 30-minute weekly session Paro intervention for 6 weeks. The control group will receive care as usual activities, such as painting, drawing, and craft, which are provided by each facility.

6. Procedure of interaction records

Participants in experimental groups will receive a group, facilitated, 30-minute weekly session of Paro intervention. A trained research assistant (RA) will give the Paro to the participants at the start of each session, repeating the same introductory script each time. The RA facilitate the participant interact with the Paro during the intervention, after 30 minutes RA will use the same ending script to end the session and goodbye to participants.

7. Outcome measures

The process and outcome of measurement will be blinded and assessed by another RA at four time points: baseline (T0), Week 3(T1), Week 6 (T2), and 1 month after the end of intervention(T3). The primary outcomes are global cognitive function and executive functions. The Mini-Mental State Examination (MMSE) will be used to assess participants' global cognitive function. The executive functions include two components such as working memory (WM) and response inhibition, which will use computerized tasks to assess the changes of executive functions for order adults before and after intervention. Working memory will be assessed using verbal WM and visuo-spatial WM tasks. Response inhibition will be assessed employing color word stroop

(CWS), stop signal (SS), and go/no-go (GNO) tasks. The secondary outcome measures are loneliness (UCLA version-3), Depression (GDS-SF), and Mental well-being (WEMWBS).

Table 2 Measurement time points and measurements

Instrument	Week-0 (T0)	Week-3 (T1)	Week-6 (T2)	Follow- up (T3)
Demographics/disease information	√			
RAAS-C	√			
Outcome measure				
-MMSE	√	√	√	√
-Executive Functions	√	√	√	√
-Loneliness (UCLA)	√	√	√	√
-Depression(GDS-SF)	√	√	√	√
-Mental well-being (WEMWBS)	√	√	√	√

Note. √, collect data; MMSE; executive function; UCLA, the University of California Los Angeles Loneliness Scale version 3; GDS-SF, Geriatric Depression Scale - Short Form; WEMWBS, Warwick-Edinburgh Mental Well-being Scale.

(1) Demographic data

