All collected data will be stored electronically with password-protection to prevent unauthorised access to the data. All data and related documents will be kept in a key-locked cabinet for 5 years before being destroyed. Although demographic data will be requested, participants will remain anonymous. For quantitative data, all data will be de-identified at data entry and results will be reported in general terms. For qualitative data, the digital interview files will be deleted after transcription. Data will be de-identified with codes and content separated. Anonymity will be maintained via pseudonyms for direct interview quotes used in the reporting of findings.

For ethical consideration, our research team will provide opportunity for the elderly in the control group who receiving plush toy. They can choose to partake two 50-minute sessions of group-based Paro interventions to experience interactions with Paro after completing their intervention and follow up.

IV. Expected difficulties encountered and solutions

1. Difficulties for participant's recruitment and active engagement data collection

This study will conduct 6 weekly sessions of Paro intervention in LTC facilities. Older adults may feel anxious about interaction with a Paro or withdraw from the

intervention. For dealing with this potential problem, the possible solutions are as below:

- (1) The research team will hold a briefing to explain the research process to the participating institutions in order to attract the participation of the heads of the institutions.
- (2) Introducing the Paro to family and encourage family and workers interacting with the Paro. Also, encouraging participants share their experiences with his/her friends.
- (3) Provide incentives or motives for participants and explaining the research procedure and potential benefits for them. The research team will show a Paro video or demonstrate Paro interaction to participants and facilities to introduce how the Paro interact with other older adults and share with experiences to using it.

2. Difficulties in quality assurance and quality control in Paro research

As a limited number of Paro, each round will plan to recruit 6 participants. The research team will extend the study periods to recruit enough participants. For controlling the research quality, the possible solutions are as below:

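### The trend analysis is given the purpose of finding the best course length, but only one course length is assigned; the data can describe the time course of the arm difference, not the optimal duration

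*Combined protocol and SAP*

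**What the plan says.** The Data analysis section of Study 3 (I.8) also covers the Study 1 biomarkers. It gives the trend analysis one purpose: "In order to identify the optimal duration of clinical application for this intervention, a trend analysis will be conducted". The sentence names no outcome, no contrast, no comparison between arms and no definition of optimal. It is not labelled exploratory, although the sentence after it, on biomarker interactions, is.

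The Intervention sections of Study 1 (II.5) and Study 3 (I.5) give the experimental group one course: "facilitated, and 30-minute weekly session Paro intervention for 6 weeks". Study 3, Expected difficulties, repeats it: "This study will conduct 6 weekly sessions of Paro intervention in LTC facilities". For the comparator, "The control group will receive care as usual activities, such as painting, drawing, and craft, which are provided by each facility". Controls may try Paro later, but only once assessment is over: "They can choose to partake two 50-minute sessions of group-based Paro interventions to experience interactions with Paro after completing their intervention and follow up".

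The note to Study 1, Table 1 dates the visits after baseline as "Week 3; O₃: Week 6; O₄: Week 10". Table 2 of each of these two studies lists four visits for every outcome except oxytocin, which is taken at baseline and week 6 only.

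**The concern.** To learn which course length works best, a trial needs participants assigned to different lengths, or an assumption that stands in for them. Here length does not vary by design. A trend over visits follows participants through a single course and for one month after it. The visit at which the effect looks largest or flattest is therefore not the same thing as the best length of programme.

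The overall abstract says the results can be promoted as a care model for long-term facilities. A statement on duration taken from the trend analysis could be carried into that model without a comparison behind it.

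**Working it through.** The plan gives no figure for this analysis, so there is nothing to reproduce. The check is whether the design identifies the stated target.

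**Step 1. Lengths assigned and observed.** The Paro arm has one length, six weeks. Controls have no Paro until follow-up is complete, and no outcome is scheduled after that. Degrees of freedom for comparing lengths = number of lengths − 1 = 1 − 1 = 0.

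**Step 2. Can different truths give the same data?** Let the Paro-minus-control effect at week t after a course of D weeks be g(min(t, D)) × exp(−λ × max(0, t − D)). All values are assumed, in SD units, for illustration only. In every model g(0) = 0, g(3) = 0.40, g(6) = 0.50, and λ = 0.05 per week after a course of six weeks or more. The models differ only where the trial has no data:

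- Model A: g(12) = 0.50; λ = 0 after a three-week course.
- Model B: g(12) = 0.50; λ = 0.5 after a three-week course.
- Model C: g(12) = 1.00; λ = 0.5 after a three-week course.

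Observed profile (D = 6) in all three: 0, 0.40, 0.50 and, at week 10, 0.50 × exp(−0.05 × 4) = 0.41.

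Implied effect at week 12:

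| Model | 3-week course | 6-week course | 12-week course |
|---|---|---|---|
| A | 0.40 | 0.37 | 0.50 |
| B | 0.00 | 0.37 | 0.50 |
| C | 0.00 | 0.37 | 1.00 |

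For example, 0.50 × exp(−0.05 × 6) = 0.37, and 0.40 × exp(−0.5 × 9) = 0.004. In A a three-week course does about as well as six; in B it leaves almost nothing; in C going on to week 12 doubles the week-6 effect. No sample size separates these models, because they agree at every visit.

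**Step 3. What is estimable.** Both arms are assessed at the same visits, so the arm differences at weeks 3, 6 and 10 can be estimated, and so can the change from week 3 to week 6. With 60 per arm, its standard error in SD units is √(2(1 − ρ)) × √(2/60), where ρ is the within-person correlation, which the plan does not give. At two-sided 0.05 and 80% power the detectable change is (1.960 + 0.842) × SE. This assumes no dropout and no clustering:

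| Assumed ρ | SE | Detectable change (SD) |
|---|---|---|
| 0.5 | 0.183 | 0.51 |
| 0.7 | 0.141 | 0.40 |
| 0.8 | 0.115 | 0.32 |
| 0.9 | 0.082 | 0.23 |

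So even the shape within the six weeks is resolved only coarsely unless the correlation is high.

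**Step 4. Oxytocin.** Two time points give one change and no shape over time.

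**Step 5. Within-arm or between-arm trend.** The same paragraph plans paired t-tests within each group and a mixed-design model for the effect of arm. It does not say which of these the trend analysis extends. A trend within the Paro arm alone would add retest and natural change to any effect of Paro.

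**The case against.** The strongest reply is that the trial does carry some information about duration. Up to week 3, a participant on the six-week course has had the same sessions as someone on a three-week course would have had. Barring anticipation, the week-3 arm difference is a randomised estimate of the immediate effect of about three sessions, and the week-6 difference does the same for about six. If optimal meant the point within the course at which benefit appears or levels off, the data would speak to it, and the plan does not define the word. This stands. A reader might infer that the data say nothing at all about duration, or that a peak at week 3 or 6 is uninformative; that goes too far.

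Three other inferences are tempting but not supported:

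- **That practice effects or calendar time could pass for an optimal duration.** Controls are assessed at the same visits, so changes common to both arms cancel in the arm difference. The risk arises only for a trend tested within the Paro arm, which the plan neither specifies nor rules out.
- **That unequal visit spacing makes the trend test wrong.** The plan names no polynomial contrast and no spacing. If equally spaced contrasts were used on a purely linear profile (0, 3, 6, 10), the quadratic contrast would be 0 − 3 − 6 + 10 = 1 rather than 0. Its sum of squares is 1²/4 = 0.25 out of 54.75, or 0.46%, which is too little to matter.
- **That the plan commits to a duration recommendation.** Duration is in none of the listed objectives, expected outcomes or contribution statements. It appears only in the purpose clause of this one sentence.

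None of this rescues the stated purpose. Onset or levelling-off within one course does not show what remains after an earlier stop or what a longer course would add.

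**Conclusion.** Wrong as written, and minor. The stated purpose cannot be met because one course length is assigned and no other is observed. Three things are out of reach: persistence after stopping at week 3, the effect of continuing past week 6, and the separation of number of sessions from time since start. Week 10 shows persistence only after the full six-week course.

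This conclusion rests on the assigned schedule and needs no assumption about effect size, SD or correlation; the SD-unit figures in the working only illustrate it. Attendance may vary in practice, but that variation is not randomised and the plan describes no attendance-based analysis. The primary comparisons are unaffected.

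**What to change.** In Study 3, Data analysis, replace the purpose clause of the trend analysis with an exploratory description of how the Paro-minus-control difference develops over time:

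- name the outcomes, and use arm-by-visit contrasts at weeks 3, 6 and 10;
- if a trend is fitted, code time in actual weeks;
- report week 10 as persistence after the six-week course;
- report oxytocin as baseline-to-week-6 change only;
- state that no conclusion on optimal programme length will be drawn.

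Before the contrasts are written, reconcile the visit labels. The Research design text of Studies 1 and 3 announces three time points, lists four and uses T2 twice, whereas the Outcome measures sections use T0 to T3.

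The cost is SAP wording and the loss of one exploratory claim. No new data or visits are needed.
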